In Parkinson's disease (PD), while motor disturbances are the predominant and most readily recognized symptoms, various non-motor symptoms frequently co-occur. Cognitive functions such as working memory and executive control are on average worse in PD, although with substantial variability across patients. This variability highlights the need for ongoing studies exploring the nature of cognitive deficits in PD and their relationship to disease severity and progression. This study utilizes pHMRI-measured dopamine buffering capacity in putative motor regions as a model of motor disease severity. We propose extending this approach to include measures of cognitive performance utilizing [the NIH Toolbox](#) [22]. The NIH Toolbox cognitive measures were chosen because they can be completed relatively quickly (important to minimize patient discomfort when assessed in the medication off state), because it incorporates tasks that directly assess functions known to be impaired in PD, and because of its recognized validity [23]. The hypothesis is that the extent of DA buffering capacity loss in pertinent regions (such as the caudate nucleus) will explain a significant fraction of the variance in specific cognitive abilities.

Secondary Aim

3. Test whether dopamine buffering capacity in caudate reflects severity of cognitive dysfunction.

STUDY DESIGN

Overall study timeline

The study is planned for complete enrollment within 3 years.

Overview of each subject's participation

After thorough clinical assessment on a screening visit, subjects return on a separate day for levodopa pHMRI. Clinical severity ratings are repeated. Regional CBF data from pre-specified brain VOIs (volumes of interest) are collected continually with ASL fMRI before levodopa, during a 10-minute i.v. loading dose, and then repeatedly over the next approximately 90 minutes.

Levodopa-naïve patients in Aim 2 will have all scan day procedures repeated identically on a second scan day after 6 ± 1 weeks of clinically dosed treatment with CD-LD.

Screening visit

1. Potential subjects will review a written informed consent document with the investigator or designee and will have opportunity to resolve questions or concerns. All procedures below are performed only after written documentation of consent.
2. We will collect the following measures at screening:
 - a. Basic demographic information
 - b. MRI safety checklist
 - c. Handedness (Edinburgh Handedness Inventory)

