Individualized for each subject based on response (benefits and side effects). Generally the starting dose will be ½ tablet by mouth twice daily, with dose increases or reductions based on contacts with the subjects as needed. Supplemental carbidopa will be prescribed for patients with prominent non-CNS side effects who have inadequate motor response (or are expected to if the dose is lowered). The plan will be not to change the dose, except for urgent clinical need, during the week prior to the second MRI scan day. See Appendix.

ANALYSIS PLAN/APPROACH/METHODOLOGY

Outcome measures

There are no outcome measures relevant to clinical care. This is not a treatment study.

Data analysis

Neuroimaging data analysis will begin with routine data preprocessing steps. ASL images will be converted to rCBF images using our previously described methods [19], weighted inversely for head motion similar to the approach of [20]. A Bayesian parameter estimation [21] procedure, with the addition of a hysteresis parameter k_e as described in Objectives above, will then be applied to repeated serum levodopa concentrations, and time–CBF curves from the volumes of interest (VOIs) listed below to estimate k_e for each VOI.

Thalamus and striatal nuclei (putamen, caudate, nucleus accumbens) will be defined from each participant's structural MR image(s) using the method of ref. [22], or if needed by FreeSurfer (<http://surfer.nmr.mgh.harvard.edu/>). Alternatively, the structures can be defined manually from the mean group atlas-aligned MPRAGE image. VOIs will be defined independent of any clinical data.

Primary VOIs:

1. Midbrain (MB). This VOI will be defined from the group difference image comparing the mean rCBF image from approximately 15-40' after the start of the LD infusion to the mean pre-infusion baseline rCBF image. The 15-40' time frame is expected to reflect activation from LD in nearly all subjects (see Fig. 2). The same time frame will be used in all subjects. The VOI will be masked to exclude voxels outside the brain. The VOI may extend into pons; comparisons to published results from 2DG and PET studies will guide any questions about defining the borders of the VOI.
2. Posterior putamen VOIs from each side of the brain (LpP, RpP). On each axial slice, a line normal to the sagittal plane and tangent to the fornix posteriorly will divide the anterior and posterior putamen, as in ref. [23]. The nucleus accumbens is excluded.

Secondary VOIs:

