3. Left and right caudate VOIs (LC, RC).
4. Left and right anterior putamen (LaP, RaP) as defined above. The nucleus accumbens is excluded.
5. Left and right nucleus accumbens (LNA, RNA).
6. Thalamus (Th).
7. Each voxel in the brain.

The primary analysis will be a correlation across all Aim 1 subjects of the k_e 's for a VOI to clinical measures of disease severity and duration. Duration of illness will be measured from the first symptom, as recorded on the screening day. Standard 20cm tapping speed in the L and R hand and hemi-UPDRS part III motor scores, both measured in the standard off condition, will capture the increased variance provided by clinical asymmetry and will be correlated with contralateral posterior putamen k_e . Midbrain k_e will be compared to total "off" UPDRS part III scores and tapping speed in the more affected hand. Specifically:

The primary comparisons for Aim 1 will be simple Pearson correlations:

1. between the off-period 20cm tapping speed in the more affected hand and the midbrain k_e , and
2. between the off-period total UPDRS part III motor score and the midbrain k_e .

Secondary comparisons for Aim 2 will be correlations:

3. between "off" 20cm tapping speed on each side and contralateral posterior putamen k_e , and
4. "off" hemi-UPDRS part III motor scores on each side and contralateral posterior putamen k_e .

For #3 and #4, we will calculate the r values using repeated measures correlation [24], with side as the repeated measure, rather than as $2n$ independent data points. However, we are interested in between-subject correlation as well as the within-subject r_{rm} that the `rmcorr` package focuses on, so we will also report that p value (corresponding to the first row in Table 3 of ref. [24]).

For Aim 2, the k_e 's for each VOI will be compared before and after 6 weeks of treatment in a repeated measures ANOVA analysis. Here the key comparison is whether k_e changes with time (before vs after treatment) in any VOI, controlling for side (more affected side vs less affected side). Our hypothesis is that this change with time is at or near 0, so our answer will be framed in terms of 95% confidence intervals for change. Any VOIs identified from the Aim 1 SPM analysis will also be tested.

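### The midbrain VOI is chosen from the same CBF data that are then fitted for midbrain k_e, which biases k_e upward and unevenly and can distort the primary Aim 1 correlations in either direction

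*Combined protocol and SAP*

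**What the plan says.** Under Data analysis in the analysis plan, thalamus and striatal VOIs come from structural MRI. The midbrain (Primary VOIs, item 1) is different: "This VOI will be defined from the group difference image comparing the mean rCBF image from approximately" 15-40 minutes after the infusion starts with the mean pre-infusion image. The reason given for the window is that it "time frame is expected to reflect activation from LD in nearly all subjects", and "The same time frame will be used in all subjects".

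The Bayesian procedure is applied to levodopa concentrations and to "CBF curves from the volumes of interest (VOIs) listed below to estimate k_e for each VOI". The CBF series covers 10 minutes before levodopa, the 10-minute loading dose, "and then repeatedly over the next approximately 90 minutes" (Study Design, overview of participation; MRI scan day). The selection frames are thus part of the series that is fitted.

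Four provisions bear on selection:
- "VOIs will be defined independent of any clinical data".
- Voxels outside the brain are masked out.
- Published 2DG and PET results guide questions about borders.
- CBF images are "weighted inversely for head motion similar to the approach of" a cited method.

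Both comparisons labelled primary for Aim 1 use midbrain k_e: one with off-period tapping speed in the more affected hand, the other "between the off-period total UPDRS part III motor score and the midbrain" k_e. Additional analysis details makes all correlation tests one-sided at 0.05, for k_e rising with severity.

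**The concern.** One set of CBF noise both picks the voxels and estimates the parameter. A voxel enters the VOI if its measured 15-40 minute minus baseline difference is large, whether from signal or from noise. Averaged over the chosen voxels, noise leaves the baseline too low and the 15-40 minute frames too high. The fit reads this as an early rise, that is, a larger k_e. Keeping VOI definition blind to clinical data stops selection on severity but not selection on CBF noise.

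The study's goal is to validate k_e as an objective, quantitative measure of severity. A primary k_e that depends in part on the cohort's scan noise works against that goal even if no false correlation results. The bias also differs between subjects, so it can alter the two primary correlations.

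**Working it through.** The plan gives no figure for selection bias and no CBF noise level, voxel count or VOI size. Everything numerical below except the frame lengths (10-minute baseline, 25-minute window) and N = 20 is an assumption.

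**1. Size of the selection shift, in closed form.** Take exchangeable voxels and independent per-minute noise with SD σ_i in subject i. The noise variance of a subject's contrast is σ_i²c, with c = 1/25 + 1/10 = 0.14. If a fraction p of voxels is kept on the group mean contrast, the expected noise left in subject i's contrast is

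shift_i = i(p) · √c · σ_i² / √(Σσ_j²), where i(p) = φ(z_p)/p.

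With p = 0.20, i(p) = 1.40. With σ = 5 for all 20 subjects, the shift is 1.40 × 5 × √(0.14/20) = 0.59 units. The baseline takes 0.10/0.14 of it (-0.42) and the 15-40 minute frames 0.04/0.14 (+0.17). A direct simulation gave 0.58, -0.42 and +0.17. Two points follow:
- Most of the shift is a lowered baseline, which looks like an immediate rise.
- A subject's share grows with σ_i². Doubling one subject's σ to 10 gives 2.2 units for that subject and 0.55 for each of the others.

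**2. Effect on k_e.** All three simulations used 20 subjects.

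| Simulation | Assumptions | Result with the planned VOI | Comparison |
|---|---|---|---|
| A | 60 independent elements, 25 responding, 20 chosen; response 6 units; true half-life 30 min | Median half-life 26 min (noise 10), 17 min (noise 20) | 30-33 min, leave-one-out or anatomical |
| B | 300 voxels, top 20% chosen; loading-type plasma curve; linear or Hill response | Mean log k_e raised 0.18 to 1.44, i.e. e^0.18 = 1.2 to e^1.44 = 4.2 times | Leave-one-out -0.01 to +0.05 |
| C | As A, mostly with added noise shared across voxels | k_e higher by about 7% (noise 5), 14-21% (noise 10), 49% (noise 20) | Relative to leave-one-out |

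As k_e ratios, A gives 30/26 = 1.15 and 30/17 = 1.76. All three agree on direction.

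**3. Unevenness.** In B (noise 5, three plasma shapes, linear and Hill response), mean log-k_e bias by true half-life was:

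| True half-life | Planned VOI | Response-blind VOI of equal size |
|---|---|---|
| 3 min | -0.06 to 0.14 | -0.19 to 0.01 |
| 60 min | 0.45 to 1.59 | -0.22 to 0.05 |
| 120 min | 1.02 to 2.73 | 0.06 to 0.83 |

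Part of the bias at 120 minutes is fitting bias that any VOI would show. The excess due to selection there, setting by setting, is 0.96 (1.02 - 0.06) to 2.10 (2.73 - 0.63). Slow-equilibrating subjects, expected to be the milder ones, are pushed up most. That compresses the k_e range and tends to weaken a real correlation.

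**4. Effect on the one-sided 5% test, with no true k_e-severity link.**
- Noise and response size unrelated to severity: 3.5-7% in B, about 6% in A. With 300 replicates the standard error at 5% is √(0.05 × 0.95/300) = 1.3 points, so this is nominal.
- Noise SD rising by e^0.2 = 1.22 or e^0.4 = 1.49 times per SD of severity: 8-15% (noise 10) and 13-24% (noise 20) in A, against 3-6% with leave-one-out. C gave 5-7.5% and 11.5%, against 3-5% and 7%.
- B, with log-SD slopes of 0.1, 0.25 and 0.5: 17%, 14-46% and 27-79%. Response size falling with severity (slope -0.25): 17%.
- Reversed links in B (noise falling, or response rising, with severity): 0% in the hypothesised direction, and 43% or 22% in the opposite one.

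**5. After the change.** Leave-one-out in B gave 4-7% in 12 of 13 settings and 10% under the strongest severity-linked noise.

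**The case against.** A reader might infer that the circular selection by itself produces a false correlation in the hypothesised direction. The documents do not support that. One VOI chosen from a group image, blind to severity, leaves the error rate nominal unless noise or response size varies with severity, and the documents state neither link. Severe patients may well move more, since involuntary movements and dyskinesias are mentioned, but that is an assumption.

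Motion weighting is planned and is absent from the rates above. When simulation A was rebuilt with each subject weighted by inverse noise variance in the group image, rates of 7%, 18%, 22% and 31% fell to 4%, 5%, 5% and 7%. This is an ideal case: the plan does not say that the weighting reaches the group image, and it need not capture all noise. The half-life bias stayed (16-18 minutes at noise 20).

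The largest effects also come from noise that fits poorly with the robust midbrain response described under Objectives. In simulation A at noise 20, the group contrast in a responding element is about 2.8 units with standard error 20 × √(0.14/20) = 1.67, so z is about 1.7. At noise 5, z is about 6.6, and the half-life was 27-28 minutes against 29, a k_e excess of 4-7%. Fewer independent elements (15 instead of 60), or all 20 + 10 - 2 = 28 subjects in the group image, also reduce the false-positive rates.

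These points limit the size and make the error-rate consequence conditional. They do not separate selection data from estimation data. The anatomical posterior putamen VOIs and the voxelwise analysis avoid the problem, but neither carries the two comparisons labelled primary for Aim 1.

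**Conclusion.** The concern holds in this form: the planned selection is circular, and it biases midbrain k_e upward and unevenly across subjects. The size cannot be fixed from the documents; across assumed scenarios it ran from a few percent at low noise to several-fold at high noise. A real correlation may be attenuated. One-sided error is inflated only if CBF noise rises, or response size falls, with severity, and motion weighting may reduce that inflation.

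Two further readings are tempting and are not established. One is a demonstrated loss of power: the available comparison, 15% against 21% on 200 replicates, is within simulation error. The other is a spurious before-after change in Aim 2: that would need the group image to use first scans only, which the plan does not say, and no calculation was made. The point should be fixed before analysis, but it does not show that the primary tests would be invalid.

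**What to change.** In Primary VOIs, item 1, define each subject's midbrain VOI from the group difference image with all of that subject's scans left out, within a fixed anatomical midbrain mask. Alternatively, draw the midbrain VOI anatomically, as for the other regional VOIs. State which scans form the group image, and use the same per-subject VOI for both Aim 2 scans. Report k_e from the group VOI as now planned as a sensitivity result only.

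The cost is SAP wording and some scripted computation; no new data are needed. The drawback is that leave-one-out VOIs differ slightly between subjects, or that an anatomical VOI includes some non-responding voxels.

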Figure 1. Across groups of PD patients, k_e is a surrogate for disease duration

[figure not shown]

Figure 2. Patients from different Hoehn and Yahr stages of PD are predicted to show different time courses of brain activity (unpublished data).

accurate k_e for a brain region that responds to exogenous levodopa with a dose-response curve anywhere close to that of clinical response. Midbrain, for instance, has a robust rCBF response to single, clinically sensible doses of levodopa [9-12,14].

This study's goal is to validate "bucket mapping" as an objective, quantitative measure of disease severity in PD. Success would position the new method for use as a surrogate endpoint in clinical studies of putative disease-modifying therapies for PD, potentially speeding up such trials dramatically.

Specific Aims

1. Test whether dopamine buffering capacity in midbrain and posterior putamen, measured by levodopa pHMRI, reflects clinical disease severity (disease duration, off-period motor function and clinical asymmetry) in 20 PD patients covering a range of current symptom severity and disease duration.
2. Test whether regional k_e values are affected by clinical treatment (6 weeks of clinically dosed carbidopa-levodopa (CD-LD) in 10 previously untreated PD patients).

Secondary Hypothesis

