predict variance of the key outcome measures and provide a formal power analysis. We have chosen the sample sizes here pragmatically, to allow recruitment and scanning at a steady, practically achievable rate. We note that the sample size of 20 for Aim 1 provides power >80% to find a moderately strong positive correlation ($r = 0.5$) while maintaining a low false positive rate $\alpha=0.05$. Power exceeds 99% to find a very strong correlation that would explain half the variance in disease severity ($r = 0.7$).

Additional levodopa-naïve subjects would not help Aim 1 substantially, as a Pearson correlation analysis is not appropriate if a large fraction of subjects are lumped at one end of the range of disease duration or severity. Therefore we plan to limit to 2 the number of subjects included in both Aims. However, if severity or duration vary substantially among the never-treated subjects, we may include more than two of them in the Aim 1 analysis. The number of subjects for Aim 2 is largely pragmatic, given the difficulty of recruitment and the additional cost with 2 scans per subject.

INCLUSION CRITERIA

There are two groups of subjects. All have idiopathic Parkinson disease. For the first group, we will attempt to sample a broad range of severity and disease duration. The second group will not be treated currently with levodopa, so most subjects in this group will be early in the disease process.

Inclusion criteria for all subjects:

- Age 40-79 at screening
- Meet accepted diagnostic criteria for Parkinson disease

EXCLUSION CRITERIA

Exclusion criteria for all subjects:

- Pregnancy
- Metal in the head or eye, or other contraindication to MRI
- Deep brain stimulator (DBS)
- Patients taking a dopamine antagonist or dopamine partial agonist
- Claustrophobia
- Significant neurologic disease other than PD (exceptions would include febrile seizures or uncomplicated migraine)
- Head trauma with loss of consciousness for more than 5 minutes
- Severe or unstable systemic illness
- MMSE < 24
- History of a primary psychotic disorder
- Current severe major depressive episode (clinical diagnosis after psychiatric interview)
- Current alcohol use disorder (clinical diagnosis after screening with the Michigan Alcoholism Screening Test)
- Current psychosis
- Subjects who feel that going without nicotine for 3-4 hours would be uncomfortable
- Currently taking an extended-release formulation of a dopamine agonist

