Additional exclusion criteria for Aim 2 subjects:

- Taking levodopa currently or in the past month, or ever for more than a month
- Taking a dopamine agonist currently

CONCOMITANT MEDICATIONS

Required:

- none

Allowed:

- Most drugs that do not prominently affect the brain or constrict blood vessels
- Loratadine and other non-sedating antihistamines
- Benzodiazepines or “Z drugs” with short half-life used in the evening only
- Medications taken only as needed (less than daily), except those listed below

PROHIBITED MEDICATIONS

Daily use of any of the following medications:

- medications containing caffeine or theophylline
- benzodiazepines with long half-lives (e.g. clonazepam), except that a single dose at bedtime for treatment of REM sleep behavior disorder may be allowed at the discretion of the PI
- centrally-active antihistamines or anticholinergics (e.g. Benadryl®)
- orally administered nasal decongestants

If taken in the 24 hours prior to the MRI scans:

- p.r.n. benzodiazepines with long half-lives, p.r.n. Benadryl®, illicit drugs

If taken on the morning of the MRI scans:

- antiparkinsonian medications
- stimulants, nasal decongestants, caffeine, nicotine, alcohol

TREATMENTS AND DOSAGE

MRI Scan day

Treatments:

- Carbidopa (Lodosyn® 25mg tablets), or FDA-approved generic equivalent
- Levodopa 2mg/ml in normal saline, as described in previous IND communications, supplied by the Barnes-Jewish Hospital Research Pharmacy service

Dose:

Carbidopa: 200mg = 8 × 25mg tablets by mouth at least 1 hour before starting the levodopa infusion

Levodopa solution: based on age and body mass as follows:

Loading dose: 0.6426mg / kg / (10 min.)

Maintenance rate: 2.882 mg/kg/min. × 10⁻⁵ × (140 year – age)/year

This is the “final dose” in Table 1 [15]. The total levodopa dose for a 60-year-old 70kg subject over a 2.5-hour infusion is 68mg; an oral dose of 80 mg would provide the same total absorbed dose, though

over a slower time scale [17]. We have used this method with the 200mg carbidopa in previous studies and reported on its safety [13,18].

Oral treatment between scan days, in the Aim 2 group

Treatment:

- Carbidopa/levodopa 25/100mg tablets (Sinemet® or FDA-approved equivalent)

Dose:

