Secondary analyses will correlate k_e 's from secondary VOIs to all measures of disease severity (off tapping speed, off UPDRS III, disease duration) and to cognitive test scores (NIH Toolbox task scores adjusted for age), using the off-period scores for measures done on the scan day. Voxelwise analyses will use SPM with an initial threshold of $t \geq 3.0$ and statistical inference at the cluster level with a false discovery rate of 0.05. Another secondary analysis will use the k_e computed from the button box tapping speeds from the more affected hand and the levodopa concentrations, independent of the perfusion MRI data ("tapping k_e "). We will test whether the tapping k_e correlates with the k_e from the midbrain or contralateral posterior putamen, or other VOIs.

Note that we expect that k_e for some VOIs will correlate better than for other VOIs with measures of disease severity or duration. This conclusion is based on the expectation that a specific clinical effect may be better associated with dopamine buffering capacity in a specific (set of) brain region(s).

Therefore we expect that the k_e -vs-clinical slope may differ significantly from zero only for a subset of the VOIs; in other words, we do not expect the slopes to be parallel across VOIs, and therefore will not include all VOIs in a single ANCOVA with a factor for VOIs. However, any errors in estimating pharmacokinetic parameters (i.e., in reconstructing the continuous function $C_p(t)$, plasma levodopa concentration as a function of time for $t \geq 0$) occur at the subject level. Such errors will affect all k_e estimates for that subject (i.e., across all VOIs). Therefore we cannot assume independence across VOIs, within subject, for the measured estimates of k_e .

Visual analog scale (VAS) measures of side effects will be analyzed as repeated measures ANOVAs. Other variables (demographics, clinical measures, NIH Toolbox scores, etc.) will be summarized or compared as appropriate using standard statistical methods.

Additional analysis details

We will examine interactions of the key analyses with subject demographics or disease variables such as age or presence of dyskinesias.

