We will use a $p=.05$ threshold for significance tests. All the correlation hypotheses are one-sided, i.e. k_e will increase with increasing disease severity or duration (e.g., positive correlation for UPDRS scores or duration, as in Fig. 1 of the attached protocol; negative correlation for tapping speed). We will not correct for multiple comparisons among the 4 numbered primary analyses named above. The secondary analyses described above involve a number of comparisons but are exploratory. We will correct individual voxelwise analyses for multiple comparisons using SPM, as described above.

For the primary analyses (correlations of k_e and disease severity or duration), outliers will be determined at the level of the individual variables before computing the correlations. If the distribution of k_e values or of disease severity markers clearly deviates from a normal distribution on visual inspection because of outlying values, after transformation if appropriate, we will use a nonparametric analysis such as a Spearman correlation.

Subjects without “off” tapping score or UPDRS will be excluded from the pertinent analyses.

Subjects without a k_e value, due to missing perfusion MRI data or missing [LD] data, will be excluded from the primary analyses. However, subjects with a few missing [LD] data points that do not prevent a good fit to the PK model will be included; an example may be a subject with missing [LD] values only between (say) 30 and 90 minutes after the infusion starts.

SAFETY MONITORING

We have recently summarized the world literature on safety of *i.v.* levodopa and no SAEs are expected [16].

The Data Safety Monitoring Plan for this protocol will consist of the following measures:

- The PI will monitor for unanticipated problems, life-threatening events and deaths.
- We will report adverse events to the Washington University Human Research Protection Office (HRPO), and in annual reports to the sponsor and the FDA.

If any SAE occurs that is judged to be probably or definitely related to participation in the study, enrollment will stop until restarting is approved by the HRPO.

REFERENCES CITED

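### Do the two primary midbrain correlations need an age-adjusted estimate beside them to support the claim about disease severity?

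*Combined protocol and SAP*

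**What the plan says.** In Data analysis, "The primary comparisons for Aim 1 will be simple Pearson correlations". The first is "between the off-period 20cm tapping speed in the more affected hand and the midbrain k_e"; the second puts off-period total UPDRS part III in place of tapping speed. Neither has a covariate, and the Spearman fallback under Additional analysis details has none either.

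The eligible range under Inclusion criteria is "Age 40-79 at screening". Additional analysis details gives the hypothesis: "All the correlation hypotheses are one-sided, i.e. k_e will increase with increasing disease severity or duration". The same section says: "We will examine interactions of the key analyses with subject demographics or disease variables such as age or presence of dyskinesias". Objectives gives the goal of validating the method "as an objective, quantitative measure of disease severity in PD".

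Age also appears in Treatments and dosage ("Levodopa solution: based on age and body mass as follows"), where the maintenance rate is proportional to 140 minus age, and in the age-adjusted NIH Toolbox scores among the secondary analyses. On pharmacokinetic error, Data analysis warns: "Such errors will affect all k_e estimates for that subject".

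Comparisons 3 and 4 in the same numbered list relate posterior putamen k_e to contralateral tapping speed and hemi-UPDRS by repeated measures correlation, with side as the repeated measure.

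**The concern.** Eligible ages span almost four decades. If older patients tend to have both a larger k_e and worse motor scores, the simple correlation is positive even when k_e says nothing about severity among patients of the same age. If age acts on the two with opposite signs, a real association is understated. Because the goal is to validate k_e as a measure of severity, a reader will want to separate these cases.

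Two features of the plan sharpen the worry. It adjusts the cognitive scores for age but not the motor comparisons. It also builds age into the infusion: the maintenance factor is 100 at age 40 and 61 at age 79, a ratio of 100/61 = 1.64, and the plan itself says pharmacokinetic errors reach every k_e of a subject. The interaction sentence does not close the gap outright, since an interaction asks whether the slope changes with age, not whether an association remains once age is held fixed.

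**Working it through.** **The plan's own power figure.** Sample size claims more than 80% power at r = 0.5 with N = 20 and alpha 0.05. A one-sided fixed-predictor noncentral t with 18 df gives 79.9%, which comes closest. The exact bivariate-normal calculation gives 75.6%. I use the exact value as the baseline below; the gap between the two is a separate matter.

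**Which hypothesis is tested.** Aim 1 and the one-sided statement say that k_e reflects, or rises with, severity or duration. Neither says independently of age. The simple Pearson correlation matches that hypothesis and holds its 5% level under it.

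**Does the dosing formula make k_e depend on age?** At 70 kg the loading dose is 0.6426 × 70 = 44.98 mg at every age. The maintenance rate is 2.882 × 10⁻⁵ × 70 × (140 − age) mg/min: 0.2017 at age 40, 0.1614 at 60 and 0.1231 at 79. Maintenance follows the 10-minute load. Check at age 60 over 150 minutes: 44.98 + 140 × 0.1614 = 67.6 mg, against the protocol's 68 mg.

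| Time from start | Age 40 | Age 79 | Ratio |
|---|---|---|---|
| 40 min | 44.98 + 30 × 0.2017 = 51.0 mg | 44.98 + 30 × 0.1231 = 48.7 mg | 1.05 |
| 100 min | 44.98 + 90 × 0.2017 = 63.1 mg | 44.98 + 90 × 0.1231 = 56.1 mg | 1.13 |
| 150 min | 44.98 + 140 × 0.2017 = 73.2 mg | 44.98 + 140 × 0.1231 = 62.2 mg | 1.18 |

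So the 1.64-fold ratio applies to the maintenance rate alone; cumulative dose differs 1.05- to 1.18-fold. Since k_e is fitted to each subject's measured levodopa concentrations, even that difference does not show that k_e varies with age.

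**How far could age move the result?** The documents give no age correlations, so these are assumptions. Let age correlate a with k_e and a with the score (signed so that positive is the hypothesised direction), with no association given age. The marginal correlation is then a². The critical r is 0.378 for Pearson (18 df) and 0.389 for the age-partial correlation (17 df). The last two columns come from simulation with 400,000 replicates.

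| a | Marginal r = a² | Simple test positive | Pearson minus partial, mean (SD) | Difference zero or wrong-signed |
|---|---|---|---|---|
| 0.2 | 0.04 | 7.0% | 0.04 (0.08) | 31% |
| 0.3 | 0.09 | 10.2% | 0.09 (0.11) | 17% |
| 0.4 | 0.16 | 16.7% | 0.16 (0.13) | 8% |
| 0.5 | 0.25 | 28.5% | 0.24 (0.15) | 3% |

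The partial test is positive in about 5% throughout. With unequal weak links (0.1 with k_e, 0.3 with the score) the simple test is positive in 6.4%; with no link to k_e, in 5%. As the marginal correlation really is above zero in every row of the table, none of these rates is a type I error of the stated test.

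**What would adjustment deliver at N = 20?**

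- If the partial r is still 0.5, power is 73.5% against 75.6% unadjusted, so the lost degree of freedom is cheap.
- If the marginal r is 0.5 and age shares part of the severity signal, the partial r is (0.5 − a²)/(1 − a²) = 0.48, 0.45, 0.40 and 0.33 for a = 0.2 to 0.5. Adjusted power is then 70%, 64%, 55% and 41%.
- The 95% interval for a partial r of 0.5 uses Fisher's z with standard error 1/√(20 − 3 − 1) = 0.25: tanh(0.549 ± 0.49) = 0.06 to 0.78.

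**What the plan already has on age.** First, an interaction model for the key analyses would normally carry an age main effect. Second, the within-subject part of comparisons 3 and 4 relates side differences in putamen k_e to side differences in motor score in the same patient. Age is constant there, and both sides share the same reconstructed plasma curve.

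**The case for a change.** The strongest reply is that nothing in the plan promises the adjusted estimate. The interaction sentence concerns effect modification and names no coefficient to be reported. Comparisons 3 and 4 concern posterior putamen, not midbrain; their lead-in calls them secondary and assigns them to Aim 2, although Additional analysis details counts four numbered primary analyses. An estimate fixed in advance is more credible than one added after the data are seen, and it would cost one sentence. Confounding can also hide a real effect: with a true partial r of 0.5 and age correlations of opposite sign at 0.2, 0.3 and 0.4, the simple test has 64%, 49% and 30% power, against about 73% for the partial.

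The textual facts and the arithmetic stand. A positive simple correlation will not by itself show that k_e tracks severity among patients of similar age. But this limits what may be concluded from a first study; it is not a fault in the test. The larger distortions need age correlations of 0.4 to 0.5 with both variables, which nothing in the documents supports, and their direction is unknown. At 0.2 to 0.3 the change on adjustment is smaller than its own sampling scatter.

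**Conclusion.** The concern does not hold. The primary correlations validly test the hypothesis as stated. Age is already named for the key analyses, and the within-patient comparisons bear on the validation claim with age held constant, though in another region. What is left is that one supporting coefficient is not promised in writing. Reporting it would change no primary test, decision rule or stated result; at N = 20 it would be imprecise and might remove real severity signal shared with age.

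On size: with assumed same-sign age correlations of 0.2 to 0.3 and no association given age, the simple test is positive in 7.0% to 10.2% of studies, for marginal correlations of 0.04 to 0.09 that truly exist. This rests on joint normality, N = 20, one-sided 0.05 and age correlations that the documents do not supply. Strong links of age with both k_e and motor score would make the adjusted estimate more informative, but the unadjusted test would still be valid for its own hypothesis.
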